Title of Project: GnRH Agonist at Embryo Transfer

Principal Investigator: [name]

Funding Source(s): Maimonides Self-Funded

1. Purpose/Specific Aims

The purpose of this study is to investigate the potential benefit of GnRH as an adjunct for in-vitro fertilization (IVF).

1.1 Objectives

We hope to demonstrate a significant difference in pregnancy and live birth rates in IVF patients who receive a GnRH agonist (Lupron) prior to embryo implantation.

1.2 Hypothesis

If a GnRH agonist is administered at the time of embryo transfer, then the success rate of pregnancy and live birth will be greater than the standard-of-care, which does not utilize this medication.

2. Background and Significance

During IVF cycles, an embryo is generally placed into the uterine cavity between 3 and 5 days after fertilization in a laboratory. For a successful pregnancy to take place, that embryo must then implant in the properly primed and staged endometrium, which subsequently must continue to develop to accommodate the growing and maturing embryo and soon-to-be fetus. This process is normally regulated by hormonal interactions between the fetal, endometrial and luteal tissue. It has been found that after embryo transfer additional support for the endometrium with progesterone improves implantation and, thus, live birth rates in IVF cycles (Van der Linden, Cochrane 2011). Recent data has shown that additional supplementation with a single administration of a GnRH agonist around the time of embryo transfer may further improve these rates (Oliveira, RepBiolEndo 2010; Van der Linden, Cochrane 2011, Ata 2008, Brigante 2013, Isik 2009, Tesarik 2006, Inamdar 2012, isikoglu 2007, Qublan 2008).

3. Research Design and Methods

This study is a randomized clinical trial. It will be a double-blinded, placebo-controlled study. On the day of embryo transfer (5-6 days after a fresh egg retrieval and on the sixth day of progesterone administration in a frozen embryo transfer cycle), patients will receive either

a single injection of 1mg of Lupron or an identical placebo injection. Patients undergoing day 3 embryo transfers will not be eligible and will not be randomized.

Randomization scheme will be computed via a computerized program accessible at randomization.com. Randomization will be in 22 blocks of 20 patients. There will be two separate randomizations, one for fresh embryo transfers and the other for frozen embryo cycles. Sequential cards with randomization allocation will be placed in doubly sealed, opaque envelopes. A single sheet confirming eligibility status and confirmation of the presence of the signed informed consent will be in the first envelope. The second envelope will be opened after there is confirmation that the patient is eligible and consented. This envelope will have a card stating the group the patient has been assigned to and blank spaces designated to record patient information. This card will be completed by the study staff and saved for reference purposes. The card will state the group that the patient was randomized to, date of embryo transfer, patient medical record number, name, and cycle type. There will also be a logbook to record the information and medication lot numbers.

Injections will be prepared at the time of randomization by a member of the study staff, and they will be administered by the clinical RN who will not know its contents. The clinical staff assessing and planning care of the patient (attending physicians and nurses) will not know the contents of the syringe (either Lupron 20IU or Saline).

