3.3 Sample Size Justification

Based on an alpha error of .05 and power of .80, with an absolute increase in LBR of 15% (consistent with earlier studies, and an overall LBR per transfer of 39.2% - from Society of Assisted Reproduction Technologies data) we will need to enroll 352 patients (176 in each group) to reach statistical significance. In order to account for attrition and the exclusion of patients moved to day 3 (earlier embryo transfer for poor embryo development), we will anticipate 20% dropout and plan to enroll 440 patients, 220 in each arm.

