3.4.4 Consent Procedures

Patients will be consented to the study any time between initiation of treatment until, and including, the day of embryo transfer. The study will be explained to the potential subject by a member of the research staff (research nurse or fellow) and not the treating physicians. The consent will be read and questions will be answered. If she wishes to enroll, the subject will sign the consent form. The study staff obtaining consent will also sign and date the consent form, and a copy will be given to the subject.

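### A published fixed block of 20, with past allocations held by study staff who are not kept apart from those obtaining consent, makes some upcoming allocations predictable

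*Combined protocol and SAP*

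**What the plan says.** Section 3 (Research Design and Methods) sets one block size: "Randomization will be in 22 blocks of 20 patients". It adds that "There will be two separate randomizations, one for fresh embryo transfers and the other for frozen embryo cycles". How the 22 blocks divide between the two lists is not stated.

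Concealment rests on envelopes: "Sequential cards with randomization allocation will be placed in doubly sealed, opaque envelopes". The order of opening is also fixed: "The second envelope will be opened after there is confirmation that the patient is eligible and consented". The allocation card carries the group, name, record number, transfer date and cycle type, and "This card will be completed by the study staff and saved for reference purposes". A logbook is kept as well, and a member of the study staff prepares each syringe. The blinded people are the attending physicians and the nurses who assess and plan care. The nurse who gives the injection is also unaware of its contents.

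On consent, Section 3.4.4 says: "Patients will be consented to the study any time between initiation of treatment until, and including, the day of embryo transfer". The study is explained "by a member of the research staff (research nurse or fellow) and not the treating physicians". The same section calls the person who obtains consent study staff, the label that Section 3 uses for those who handle the allocations. Section 5 places randomization at the time of transfer, and Section 3.2 makes this a single-site trial.

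**The concern.** A sealed envelope stops anyone from reading the next card. It does not stop anyone from inferring it. If the block size is known and past allocations in the list are recorded in clear, the places left in the current block give the odds for the next woman, and near the end of a block they can give the answer. With one site, one team can see the whole sequence, and because the card records cycle type, a tally for each list is easy to keep.

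If the person with that tally also obtains consent, he or she could decide whether to approach a particular woman in the light of the likely arm. Prognosis could then differ between arms before randomization. Blinding of the treating staff protects care after allocation, and live birth is an objective outcome, but neither protects against selection at entry.

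**Working it through.** **Inputs from the documents.** Block size 20 and 22 blocks (Section 3). Section 3.3 gives 176 evaluable per group (352 in all), 20% dropout, a reference live birth rate of 39.2% and an absolute increase of 15 points, and says "plan to enroll 440 patients, 220 in each arm".

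**The plan's own figures.** 352 / 0.80 = 440, and 22 × 20 = 440, so blocks and sample size agree. Taking 39.2% as the control rate (54.2% on treatment), a two-sided 5% test at 80% power needs 173 per arm by the pooled formula without continuity correction, close to the stated 176. Power at 176 per arm is 80.8%. The point does not affect the sample size.

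**Assumption.** Each block holds 10 of each arm. The equal arms imply this, but the protocol does not state it.

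**Certain allocations.** For a block of 2m, the expected number fixed by the tally is 2m/(m + 1). With m = 10 this is 20/11 = 1.82 per block. 1.82/20 = 9.1%, and 22 × 1.82 = 40 of 440.

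**Correct guesses.** Someone who always names the arm with more places left is right on average m + (4^m / C(2m, m) − 1)/2 times per block. With m = 10: 10 + (1,048,576/184,756 − 1)/2 = 12.34. 12.34/20 = 61.7%, against 50% by chance.

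**From predictability to bias (steering is assumed).** Let d be the difference in live-birth chance between women steered to slots guessed as Lupron and those steered to slots guessed as saline.

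- Every guess acted on: bias = (2 × 0.617 − 1) × d = 0.234d.
- Only certain slots acted on: bias = 0.0909d.
- Every guess acted on, but only among the share of women who consent late: bias = share × 0.234d. The documents give no share; 25% is used for illustration.

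**Effect on the test.** With the average of the two design rates, (39.2 + 54.2)/2 = 46.7%, in both arms and 176 per arm, the standard error of the difference is √(2 × 0.467 × 0.533/176) = 5.3 points. Type I error is the two-sided 5% rejection probability of a normal statistic shifted by bias/SE.

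| Steering (assumed) | d (points) | Bias (points) | Type I error |
|---|---|---|---|
| Every slot | 5 | 1.2 | 5.6% |
| Every slot | 10 | 2.3 | 7.2% |
| Every slot | 15 | 3.5 | 10.1% |
| Certain slots only | 10 | 0.9 | 5.3% |
| Every guess, 25% consent late | 10 | 0.6 | 5.1% |

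**What other block schemes would do.** Sizes drawn at random from 12, 16, 20 and 24 were simulated against a guesser who knows the possible sizes but not the realised ones. About 0.5% of allocations stay certain, and guessing is right about 62% of the time. A fixed block of 4 is worse than the present plan: 33.3% certain and 70.8% guessed correctly.

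**The case against.** The strongest reply is that the route to bias is narrow.

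- Consent may be taken from the start of treatment, and a woman who has already consented cannot be selected at that step on the day of transfer.
- The cycle sets the transfer date, so moving a woman to a later slot is not a free choice.
- The visible eligibility criteria (age 18 to 40, no day 3 transfer) leave little discretion.
- Treating physicians neither obtain consent nor know the allocation.
- Section 5 plans logistic regression for baseline differences, which would recover part of any imbalance in recorded factors, though it names none.
- Twenty is already a long block, and varying its length hardly changes the guess rate.

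All of this stands. It limits the likely size of the harm and shows that block length is not the main defect. It does not remove the predictability, which follows from a fixed, published size and a visible tally, nor does it protect against imbalance in unrecorded factors.

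A reader might infer more than the documents support:

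- **That the same person sees allocations and obtains consent.** The text neither says nor excludes this. Section 3.4.3 was not in the text available to this review and may bear on it.
- **That consenting staff know embryo quality.** Nothing says so. That they can judge prognosis, and would act on it, is an assumption.
- **That the trial's type I error is 7.2% or 10.1%.** Those figures require every slot to be steered.
- **That the double blind fails.** The point concerns entry to the trial, not care or assessment afterwards.

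**Conclusion.** The concern holds as a weakness in allocation concealment that is cheap to close. Given 10:10 blocks and knowledge of the tally, 9.1% of allocations are certain and 61.7% can be guessed. This follows from the stated design and needs no assumption about anyone's conduct.

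The bias does need such assumptions. At a 10-point difference in prognosis it ranges from about 0.6 to 2.3 points across the scenarios shown, against a design effect of 15 points. The upper end assumes that every woman can be steered, which early consent makes unlikely. The lack of a stated separation of roles matters more than the block size, because only separation acts on the guess rate. The documents show an open route for selection; they do not show that selection would occur.

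**What to change.** **Main change, Section 3.4.4.** State that whoever opens the second envelope, keeps the cards or logbook, or prepares syringes does not obtain consent or confirm eligibility, and that those who do so have no access to the allocation records. The research nurse and the fellow already named could divide the tasks, with the eligibility and consent sheet completed by one and handed to the other. For those obtaining consent, this returns guessing to 50%. The cost is one sentence and a fixed assignment of roles among existing staff.

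**Supporting change, Section 3.** Replace the fixed block of 20 with permuted blocks of randomly varied but similar length (for example 12, 16, 20 or 24), drawn separately for the fresh and frozen lists, with the sizes kept out of the protocol and withheld from study staff. This cuts certain allocations from 9.1% to about 0.5% but leaves guessing at about 62%, so it does not replace the main change. Small blocks should be avoided. The cost is a regenerated list and a possible end-of-list imbalance of 12 rather than 10 in each list. Sample size, treatment and follow-up are unaffected.

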3.1. Duration of Study

The study will last two years.

3.2 Study Sites

All embryo transfers are performed at the Maimonides-affiliated, Genesis Fertility office located at [name]. This will be the only site for the study.

3.3 Sample Size Justification

Based on an alpha error of .05 and power of .80, with an absolute increase in LBR of 15% (consistent with earlier studies, and an overall LBR per transfer of 39.2% - from Society of Assisted Reproduction Technologies data) we will need to enroll 352 patients (176 in each group) to reach statistical significance. In order to account for attrition and the exclusion of patients moved to day 3 (earlier embryo transfer for poor embryo development), we will anticipate 20% dropout and plan to enroll 440 patients, 220 in each arm.

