3.4.2 Exclusion Criteria

Patients with day 3 embryo transfers will be excluded.

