4.4 Potential for Benefit

Studies in humans have shown that using Lupron increases pregnancy and live birth rates during IVF. The formulation and dose of Lupron used in this study is short acting and is metabolized and excreted from the body before implantation occurs.

5. Data Handling and Statistical Analysis

A computer-generated list of random numbers will be used for randomization. Patients will be randomized at the time of embryo transfer.

All databases will be de-identified. The identification key will be kept in a locked cabinet in the office of Genesis Fertility.

The study will take 2 years for recruitment and treatment, and 1 subsequent year for follow-up data collection (live birth status after treatment) and analysis.

Endpoints were listed above and are the gold standard for IVF experiments.

A univariate chi square analysis will be used to compare the two treatment groups with regard to percent of rate of live births in each group. Logistic regression will be used to compare rates in the treatment groups as a function of live transfer versus frozen embryo to determine any interaction effect due to type of transfer. Logistic regression will also be used to control for the possibility of any differences or confounding factors at baseline. A similar analysis plan will be used for the secondary outcomes.

6. Data and Safety Monitoring

Interim analyses will be performed after each 50 patients enrolled to ensure non-maleficance. Block analysis will ensure there is no bias at these interim analyses. We have a Data Safety and Monitoring Board who will be performing the block analyses.

Analysis will include assessment and statistical comparisons of clinical pregnancy rates, ongoing pregnancy rates, live birth rates, and any other complications, including hospitalizations, infections and miscarriage rate. Any significant difference in these outcomes at an interim analysis will trigger cessation of the study, and a complete report will be provided to the IRB that includes all clinical and research data collected in the study.

7. Reporting Results

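### Does the single 20% allowance, covering both day-3 exclusions and attrition, leave the target of 440 undefined?

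*Combined protocol and SAP*

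**What the plan says.** Section 3.3 derives 352 women (176 per group) from a 5% alpha, 80% power, a live birth rate of 39.2% and an absolute gain of 15 points. It then makes one addition for attrition and for women whose transfer is brought forward to day 3: "we will anticipate 20% dropout and plan to enroll 440 patients, 220 in each arm".

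The other relevant statements are:

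- Section 3 on day-3 transfers: "Patients undergoing day 3 embryo transfers will not be eligible and will not be randomized". Section 3.4.2 repeats it: "Patients with day 3 embryo transfers will be excluded".
- Section 5 on timing: "Patients will be randomized at the time of embryo transfer".
- Section 3.4.4 on the consent window: "Patients will be consented to the study any time between initiation of treatment until, and including, the day of embryo transfer". On the act of joining: "If she wishes to enroll, the subject will sign the consent form".
- Section 3 on the allocation list: "Randomization will be in 22 blocks of 20 patients".
- Section 6 on monitoring: "Interim analyses will be performed after each 50 patients enrolled".

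**The concern.** A woman who consents early in her cycle and is then switched to day 3 leaves before she has an arm. She cannot be among those lost between 220 and 176 in an arm, yet section 3.3 counts her in the allowance that produces the 220. The consent section, which links enrolling to a signature, adds to the doubt. On one reading 440 women sign and fewer are randomised. On the other, 440 are randomised and more may have to sign.

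Three things could be at stake: whether the trial reaches its stated power, how many women staff must approach, and when each interim look falls, since that is counted in women enrolled.

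**Working it through.** **Inputs.** From section 3.3: alpha 0.05, power 0.80, 39.2% (read as the control rate), a gain of 15 points (so 54.2%), 352 before and 440 after the allowance, and 20% loss. From section 3: 22 blocks of 20. Two-sided testing is assumed, because the plan does not state sidedness. The day-3 shares used below are assumptions, because the plan gives none.

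**1. The plan's base figure.** Pooled two-proportion formula, with mean rate 0.467:

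n per arm = [1.960 × √(2 × 0.467 × 0.533) + 0.842 × √(0.392 × 0.608 + 0.542 × 0.458)]² / 0.15²

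The two roots are 0.7056 and 0.6975, which gives 172.5, or 173 per arm and 346 in total. The plan's 352 is within 2% of this and slightly on the safe side.

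**2. The inflation.** 352 / (1 − 0.20) = 440, or 220 per arm. This divides by the retained fraction, as it should. Multiplying by 1.2 would have given 423.

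**3. Power by evaluable number.** Power = Φ[(0.15√n − 1.960 × 0.7056) / 0.6975]

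| Evaluable per arm | Power |
|---|---|
| 176 | 0.808 |
| 198 | 0.852 |
| 209 | 0.870 |
| 220 | 0.886 |

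**4. If 440 counts randomised women.** Day-3 switches do not touch the arms. The whole 20% is available for later loss, and 440 × 0.80 = 352 remain in the worst planned case. Power is 0.808 or better. If every woman consented before her day of transfer was known, the consents needed would be 440/0.95 = 464, 440/0.90 = 489 or 440/0.80 = 550 (rounded up) at assumed day-3 shares of 5%, 10% or 20%. Consent on the day of transfer, which section 3.4.4 allows, brings this back to about 440.

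**5. If 440 counts consents.** The same shares leave 418, 396 or 352 randomised. If total loss is 20%, 352 remain however it is divided: with 10% to day 3 and 11.1% later, 440 × 0.90 × 0.889 = 352. Power is again 0.808.

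**6. Which reading the text supports.** Only randomised women have an arm, so the per-arm figure in section 3.3 describes randomised women. The block plan gives 22 × 20 = 440, the same number. (Section 3 also describes separate fresh and frozen lists without saying whether 22 blocks is the total, but the match with 440 suggests that it is.) The sentence in section 3.4.4 is procedural and sets no count.

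**7. Interim looks.** Counted by consent, a look at 50 would hold 50 × 0.95 = 47.5 or 50 × 0.90 = 45 randomised women at assumed shares of 5% or 10%. These looks compare outcomes between groups, which exist only for randomised women, so the natural count is randomised women.

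**The case for a change.** The best case for a change is that the 80% claim is secure only while combined loss stays within 20%, and the plan never divides that figure. If 440 were consents and losses compounded to more than 20%, power would fall. With 20% to day 3 and 10% later, 440 × 0.80 × 0.90 = 317 women are evaluable and power is about 0.77. If unknown births were counted as no live birth, 220 per arm with 20% attrition would compare 31.4% with 43.4%, at power of about 0.74.

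Little of this bears on the wording of section 3.3. The first case exceeds the plan's own allowance, and any sample size fails when its loss assumption is exceeded. It also applies a 20% day-3 share to all women. Section 3.3 attributes the switch to poor embryo development, which naturally describes fresh cycles, while frozen transfers are timed to the sixth day of progesterone. If half the women had frozen cycles (an assumption), 20% overall would mean 40% of fresh cycles. The second case depends on a rule for missing outcomes that the plan does not state. That is a separate question, and labelling 440 differently would not answer it.

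Nor does the plan say that attrition falls only after randomisation. A withdrawal between consent and transfer would also be attrition, so the two losses may overlap in time more than the concern supposes. What stands is that section 3.3 is loosely worded and that no consent target is given.

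**Conclusion.** No change follows. The pooled allowance is an imprecision in wording, not an error in the sample size. The base figure reproduces to within 2%, the inflation is exact, and the per-arm count and block plan both indicate 440 randomised. Stated power is met under either reading, from 0.808 at 176 evaluable per arm to 0.886 at 220. This rests on total loss of 20% or less, analysis of women with known outcomes, a two-sided test and 39.2% as the control rate.

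The unstated consent count is an operational number that staff can settle as recruitment proceeds, and consent on the day of transfer keeps it near 440. An analyst or monitoring board would count randomised women without being told. Splitting the 20% would leave the number randomised, the test and the conclusions as they are.

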3.4 Subject Selection and Enrollment Considerations

3.4.1 Inclusion Criteria

Women undergoing IVF/ICSI or frozen embryo transfers (FET) between the ages of 18 and 40 years old will be included.

3.4.2 Exclusion Criteria

Patients with day 3 embryo transfers will be excluded.

3.4.4 Consent Procedures

Patients will be consented to the study any time between initiation of treatment until, and including, the day of embryo transfer. The study will be explained to the potential subject by a member of the research staff (research nurse or fellow) and not the treating physicians. The consent will be read and questions will be answered. If she wishes to enroll, the subject will sign the consent form. The study staff obtaining consent will also sign and date the consent form, and a copy will be given to the subject.

